The Effect of Vibration on Pain during Intravenous Injection of Propofol: A Randomized, Controlled, Single-blinded Study

Registered United States Food and Drug Administration (FDA) Clinical Trial (NCT #03509857)

Document last updated: February 16, 2022

Background and Significance

Infusion of propofol during the process of inducing anesthesia can cause a fair amount of transient discomfort to patients while they are on the operating table. It is not uncommon for patients to cry out in pain. The investigators have noticed this first hand on numerous occasions and have wondered if there is a risk-free way to lessen the pain associated with propofol infusion.

This study will focus on the use of vibration analgesia to potentially reduce the pain associated with propofol infusion. Vibration is proposed to stimulate A-beta nerve fibers, which transmit information from vibration and touch which, according to the Gate Control Theory of Pain (Melzack and Wall 1965), inhibits signal transduction by A-delta and C fibers (Kakigi and Shibasaki 1992). Vibration has been demonstrated to be effective in decreasing pain during vaccinations, phlebotomy, and dental anesthesia (Baxter et al. 2011; Nanitsos et al. 2009).

In this study, we seek to evaluate the role of vibration in the reduction of discomfort associated with painful stimulus during anesthesia induction. Through this study, we hope to develop a comprehensive and cost-effective approach to minimize patient discomfort during anesthesia induction.

Study Design

The objective of this study is to evaluate the effectiveness of vibration as an analgesic during induction of anesthesia. It is our hypothesis that vibration will lessen the pain of propofol infusion.

Patients who are set to receive a propofol infusion as part of induction of general anesthesia during surgery will be recruited to participate in this study. All participating patients will be randomized following acquisition of consent for study participation to one of two intervention groups: 1) normal standard of care infusion of propofol without vibration analgesia 2) infusion of propofol with application of vibration analgesia prior to infusion. The amount of pain perceived by patients during the infusion will be analyzed via two methods: first the commonly utilized visual analogue scale (VAS) as well as the more objective four-point pain manifestation scale (J.-R. Lee et al. 2007, Grauers et al. 2002). Patients will be asked to place a mark on a 10-cm visual analogue scale corresponding to the level of pain that they experienced during the infusion, as commonly utilized in previous studies. Additionally, two trained study investigators (one blinded to treatment group) will document the subject's perceived maximum pain/discomfort using a four-point pain manifestation scale as outlined in previous pain studies: (1) "severe" pain if pain manifests as verbal response accompanied by facial grimacing or withdrawal of arm, (2) "moderate" pain if grimacing or arm withdrawal is not accompanied by verbal response, (3) "mild" pain if within 30 seconds, severe or moderate pain is not observed, the patient is asked whether they had any discomfort in the arms and they answer 'yes,' (4) "no"- pain if within 30 seconds, severe or moderate pain is not observed, the patient is asked whether they had any discomfort in the arms and they answer 'no.'

Due to constraints regarding the validity of the linear visual analogue scale in very young patients (Stinson et al. 2006), only adults who are able to consent for themselves will be eligible for participation in the study.

Exclusion criteria include minors and pregnant individuals.

The primary outcome will be the level of pain reported by the patient immediately following propofol injection, with or without a vibration analgesia adjunct. Secondary outcomes will include subgroup analysis for responses in pain as stratified by pathology, age, sex, and ethnicity.

Intervention

Patients will be randomized to one of two treatment groups. Randomization will be performed by placing equal numbers of indicators for each treatment group in opaque, sealed envelopes, which will be shuffled. The surgeon will have access to a kit which contains these envelopes. One card will be selected in sequence from the pre-shuffled stack for each patient who gives consent to participate in the study.

The intervention group will receive vibration only, with application of the BUZZY device just proximal to the intravenous infusion site immediately before and during propofol infusion. Propofol will be administered according to the institution's standard weight-based dosing (2 mg/kg) infused over 3 minutes, repeated as needed to achieve the desired sedation level.

Immediately following intervention, patients will be asked to rate the discomfort of the infusion on both a Numeric Rating Scale, with a number between 0 and 10, and a Visual Analogue Scale, by placing a mark on a continuous 10-cm line corresponding to their level of perceived pain. Additionally, two trained study investigators (one blinded to treatment group) will document the subject's perceived maximum pain/discomfort using a four-point pain manifestation scale as described in the above "Study Design" section. These values will be used to compare efficacy between each intervention arm as described in the Statistics section.

With regards to safety outcomes, no significant safety issues are anticipated beyond those inherent to established practice.

Response cards will not contain any identifiable patient information and will be linked to consent forms only through a numerical key. Consent forms will be stored separately in a secured in-hospital location following each patient interaction.

Intervention will be performed in the operating room during general anesthesia induction, as indicated, following acquisition of patient consent and randomization to a treatment arm as described above. Only a single intervention will be performed. Routine office follow-up will be offered to each patient for longitudinal management of any potential harms.

Population

Patients will be recruited from Montefiore Medical Center, Hutchinson ambulatory surgery center in the preoperative holding area prior to their surgery.

The study sample size will need to be approximately 100 patients, 50 in each treatment arm, to achieve a power of 80% to detect a difference of 10 mm on the Visual Analogue Scale between any two study arms. This was based upon a previous study (Nakayama et al. 2001) which demonstrated a mean reduction in discomfort between buffered and unbuffered lidocaine of 1.0 on the Numeric Rating Scale (from 3.5 to 2.5, with a SD of 1.4).

Given that the study involves a single interaction, there is no dropping out from the study or loss-to-follow-up anticipated.

Inclusion and exclusion criteria are described in the above sections. Specifically, however, minors may not be recruited into the study, as the Visual Analogue Scale is not considered reliable for that age group (please see Study Design section).

The consent form will be provided in English, and will be reviewed via translation phone for non-English-speakers, provided that the treating or examining physician is not fluent in the patient's preferred language.

No tissue specimens or blood samples will be obtained from participating patients. Recruitment

Patients will be recruited into the study by the surgeon prior to their operation. No additional recruitment materials will be utilized. The study will be explained in-person and consent obtained with appropriate documentation. Privacy will be protected by keeping the consent documentation in a separate, locked, secure location from the response cards.

Informed Consent

The informed consent form in use for this study is based upon the Einstein IRB recommended template and has been included with this study application.

Informed consent will be obtained in the preoperative holding area where the patient is spoken to by both the anesthesiologist and surgeon. Eligible patients will be given the opportunity to enroll in the study after it has been determined that they will receive propofol infusion as part of their general anesthesia.

If they prefer to forgo study participation, they will receive the Standard Treatment and will not be enrolled; no information from the encounter, except a running count of individuals who refused to participate, will be recorded for use in the study. There is no requirement for a waiver of informed consent.

This study will be performed without additional cost to participating patients and no remuneration will be offered for participation.

Numerical Rating Scale (NRS) of pain, as reported by patients immediately following infusion of propofol as well as those perceived by study investigators as detailed above. The NRS, although not necessarily as reliable as the VAS, is a single whole number, which cannot be subject to interpretation by the examiner. The VAS is measured from a value of 0-10cm along a continuous line, and the patient is asked to place a mark on the line at a point at which, they feel, corresponds to the level of their pain. This value will be measured by a third, independent investigator not otherwise involved in the study.

Following acquisition of the NRS and VAS pain values, these values will be entered in the study database, which will be maintained solely by the primary investigators, keyed to individual participants' consent forms by a non-identifying serial number. Again, the consent forms will be stored in a separate location. Given the single site and relatively small size of study subjects, close monitoring by the study investigator is an adequate level of monitoring for this advice, as outlined and described in the DSM policy. 31 March 2018

All statistical analyses will be reviewed and verified with a faculty statistician.

Results

A total of 100 participants were recruited between April 2019 and November 2019, 50 in each study arm (control versus treatment group) with no losses or exclusions after randomization; recruitment was stopped once the calculated sample size was obtained. The control group and treatment group were comparable with respect to demographic characteristics. The mean age of patients was 50.8 ± 13.9 years. 39% of patients were males. The mean patient BMI was 28.5. Agreement between the attending anesthesiologist and CRNA observers regarding pain scores (scale from 0 to 3 points) was excellent and statistically significant, with weight kappa (κ_w) = 0.82 ($p < 0.001$).

A significantly lower incidence of pain was found in the treatment group as compared to the control group. Nine (18.0%) patients in the treatment group had pain during propofol injection as compared to nineteen (38.0%) patients in the control group ($p = 0.03$), yielding a risk difference of 20.0%. Significantly lower severity of pain was found in the treatment group as compared to the control group. The median summative pain score (scale: 1-6) in the treatment group was 1 [IQR: 1-2] as compared to 2 [IQR: 2-4] in the control group ($p < 0.01$).

The Effect of Vibration on Pain during Intravenous Injection of Propofol: A Randomized, Controlled, Single-blinded Study

Registered United States Food and Drug Administration (FDA) Clinical Trial (**NCT #03509857**)

Document last updated: February 16, 2022

Statistical Analysis Plan

All analyses will be computed using Stata v16.0 (College Station, TX: StataCorp LLC). Bivariate analyses will be performed using independent sample t-test, Mann-Whitney test, chi-square, Fischer's exact test, or Spearman correlation; multivariable analysis will be performed using log-binomial regression in order to evaluate the association between treatment group and pain outcome while adjusting for potential confounders. Variables with $p < 0.20$ on bivariate analysis will be added to the model in backwards elimination fashion and will be kept in the model if they are found to alter the association between treatment group and pain outcome by more than 10%, or if they possess an independently significant association with pain outcome. All first order interactions will be assessed. Linearly weighted kappa will be used to evaluate inter-rater agreement. Statistical significance will be set at $\alpha < 0.05$.

Results

Outcomes

A total of 100 participants were recruited between April 2019 and November 2019, 50 in each study arm (control versus treatment group) with no losses or exclusions after randomization; recruitment was stopped once the calculated sample size was obtained. The control group and treatment group were comparable with respect to demographic characteristics. The mean age of patients was 50.8 ± 13.9 years. 39% of patients were males. The mean patient BMI was 28.5. Agreement between the attending anesthesiologist and CRNA observers regarding pain scores (scale from 0 to 3 points) was excellent and statistically significant, with weight kappa (κ_w) = 0.82 ($p < 0.001$).

A significantly lower incidence of pain was found in the treatment group as compared to the control group. Nine (18.0%) patients in the treatment group had pain during propofol injection as compared to nineteen (38.0%) patients in the control group ($p = 0.03$), yielding a risk difference of 20.0%. Significantly lower severity of pain was found in the treatment group as compared to the control group. The median summative pain score (scale: 1-6) in the treatment group was 1 [IQR: 1-2] as compared to 2 [IQR: 2-4] in the control group ($p < 0.01$).

A higher incidence of pain with propofol infusion was noted in patients with an intravenous catheter location in the hand as compared to other locations with a risk ratio of 2.7 (95% CI: 1.07-6.97, $p = 0.04$). A log-binomial regression analysis was performed adjusting for the intravenous catheter location. A significantly lower incidence of pain in the treatment group versus the control group was maintained in the regression analysis with a risk ratio of 0.44 (95% CI: 0.22-0.86, $p = 0.02$).

The propofol dose did not differ significantly between the treatment and control groups and did not differ significantly in patients with or without pain ($p = 0.95$ and $p = 0.30$, respectively).

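### As worded, the severity result (summative score 1 [1-2] vs 2 [2-4], scale 1-6) does not fit the incidence result beside it (9/50 vs 19/50); the score, its denominator and the rule for counting pain need defining

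*SAP*

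**What the plan says.** The SAP (Results, Outcomes) and the Protocol (Results) carry the same sentences.

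- Denominator: "50 in each study arm (control versus treatment group) with no losses or exclusions after randomization".
- Incidence: "Nine (18.0%) patients in the treatment group had pain during propofol injection as compared to nineteen (38.0%) patients in the control group", with p = 0.03 and a risk difference of 20.0%.
- Severity: "The median summative pain score (scale: 1-6) in the treatment group was 1 [IQR: 1-2] as compared to 2 [IQR: 2-4" in control, with p < 0.01. No n is given for this comparison, and it is worded as a contrast of the two groups.
- Rating scale: "Agreement between the attending anesthesiologist and CRNA observers regarding pain scores (scale from 0 to 3 points", followed by a weighted kappa of 0.82.

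The Protocol (Study Design) describes a four-category observer scale (severe, moderate, mild, none) and says "two trained study investigators (one blinded to treatment group) will document" the rating. Under Intervention it adds self-report: "patients will be asked to rate the discomfort of the infusion on both a Numeric Rating Scale" and a visual analogue scale. Neither document says how the summative score is formed, which patients enter it, or which measure and cut-off decide that a patient had pain.

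**The concern.** The two efficacy contrasts stand next to each other and appear to describe the same 50 patients per arm. On the plain reading, where a patient without pain sits at the lowest score and anyone above it had pain, most patients in each arm would be at the floor. Quartiles of 1 [1-2] and 2 [2-4] look too high for that.

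At stake is what the claim of significantly lower severity means. If the medians come only from patients who had pain, they compare 28 people selected by an outcome that arose after randomisation, and they do not describe the arms. If they come from everyone, then the 18% and 38% rest on a rule that leaves some patients with non-zero scores outside the pain count, and the reader needs that rule to interpret the incidence.

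**Working it through.** **Inputs** (SAP, Results, Outcomes; repeated in Protocol, Results): n = 50 per arm; pain in 9 and 19; summative score 1 [1-2] and 2 [2-4]; printed scale 1-6; observer scale 0-3; severity p < 0.01. The SAP names Stata, so Stata's default percentile rule is used. Tests are taken as two-sided.

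**1. The incidence result reproduces.**
- Risk difference: 19/50 − 9/50 = 0.38 − 0.18 = 0.20.
- Pearson chi-square: 100 × (9×31 − 41×19)² / (50×50×28×72) = 100 × 500² / 5,040,000 = 4.96, p = 0.026, which rounds to the printed 0.03. Fisher's exact test gives p = 0.044.

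**2. Patients needed by the printed quartiles, with n = 50.** The lower quartile is the 13th ordered value (50 × 0.25 = 12.5, rounded up). The upper quartile is the 38th (50 × 0.75 = 37.5, rounded up).

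| Arm | Printed quartile | Ordered values that must be 2 or more | Patients needed | Patients with pain |
|---|---|---|---|---|
| Treatment | Upper = 2 | 38th to 50th | 13 | 9 |
| Control | Lower = 2 | 13th to 50th | 38 | 19 |

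Other percentile definitions move the needed counts by about one. The gaps are 4 and 19.

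**3. What the plain reading would give.** Treatment has 41/50 = 82% at the floor, so all three quartiles equal the floor. Control has 31/50 = 62% at the floor, so its lower quartile and median equal the floor. The conflict is present in both arms, whether the floor is 0 or 1.

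**4. The scale.** Two ratings of 0-3 sum to 0-6. The printed range is 1-6.

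**5. Reading A: medians in patients with pain only (n = 9 and 19).** A range of 1-6 fits, because zeros are left out. There are 30 score distributions on 1-6 for n = 9 and 1,125 for n = 19 that match the printed quartiles.
- Restoring 41 and 31 zeros gives treatment 0 [0-0]. In control, the 38th of 50 values is the 7th of the 19 pain scores. The 5th (lower quartile) and 10th (median) are both 2, so the 7th is 2, and control is 0 [0-2].
- Mann-Whitney tests (tie-corrected normal approximation) over all 30 × 1,125 pairs, matching the quartiles alone: all-50 p from 0.005 to 0.019; subset p from 0.0002 to 0.31.
- Adding the printed p < 0.01: if it came from the 9 vs 19 subset, the all-50 p lies between 0.005 and 0.0097. If it came from all 50, the subset p is at most 0.021.

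These are ranges over feasible data, not probabilities.

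**6. Reading B: all 50 per arm, pain defined by a cut-off on the sum.** The control median (25th and 26th values) is 2 and belongs to the 31 without pain, so the cut-off must exceed 2. The control upper quartile (38th value) is 4 and belongs to the 19 with pain, so the cut-off cannot exceed 4. A cut-off of 3 or more, or 4 or more, fits control, and both also fit treatment. A rule based on one observer's rating or on self-report is a further possibility. If the score is the sum of the two ratings, the range on this reading should be 0-6.

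**The case against.** The strongest reply is that nothing here is miscalculated. The incidence p-value reproduces, and each of the two readings makes the severity figures attainable. If a cut-off of 3 or 4 was used on all 50, the medians do describe the randomised arms, and the faults reduce to an unstated cut-off and a range printed as 1-6. That stands: the preference for the pain-only reading rests on the missing zero in the range, which could be a misprint.

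A second reply is that the significance claim is not in danger. This also stands. A reader might take the wide subset range, up to 0.31, as a sign that the severity result could be null. The printed p < 0.01 rules that out under the pain-only reading: the all-50 p is below 0.01 in every feasible case if the printed value came from the subset, and if it came from all 50 the test has already been done.

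Neither reply removes the inconsistency. If the score is the sum of the two ratings, either the denominator implied by the wording or the printed range is wrong, and the text does not say which.

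**Conclusion.** The concern holds as an inconsistency in reporting that should be corrected. If any score above the floor counts as pain, the severity and incidence results cannot both describe 50 patients per arm: 13 needed against 9 in treatment, and 38 against 19 in control. This assumes Stata's percentile rule, but the gaps are larger than any change of definition could close. The point about the range assumes that the summative score is the sum of the two 0-3 ratings.

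Two stronger inferences are not supported. A reader might conclude that the medians were certainly taken from patients with pain only; that fits the 1-6 range, but no sentence says so. A reader might also conclude that the incidence depends on one observer. On the pain-only, summed reading, a median of 1 among 9 does mean that at least 5 treated patients were rated 0 by one observer. However, nothing in the documents proposes that both observers had to record pain, so no alternative incidence follows.

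Under the pain-only reading, the direction and significance of the severity result survive. What fails is the printed pair of medians as a description of the arms, which would be 0 [0-0] and 0 [0-2].

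**What to change.** In the Results of both documents:

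- State the rating codes, how the summative score is formed, and its true range.
- State the rule and source (observer rating or self-report) for counting a patient as having pain.
- Give the n per arm for the severity result.
- Base the severity claim on a Mann-Whitney test of the observed summative score in all 50 per arm, with 0 only where both observers rated 0, and report the count at each score by arm. Patients outside the pain count should not be set to 0 automatically, because under a threshold or self-report rule that would overwrite real non-zero scores.
- If the printed medians come from patients with pain only, label them as descriptive, among patients with pain, 9 vs 19.
- If a threshold or self-report rule was used, state it, reword the incidence sentence to match, and correct the range.

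The cost is a few definitions, one corrected sentence in each document, and at most one re-run test on existing data. The downside is that the contrast in medians may disappear (both are 0 under the pain-only reading), so the counts by score would have to carry the description.
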